## **A. SPECIFIC AIMS**

- 1. Aim 1. Determine the effects of a 4-week course of anti-inflammatory supplementation (PolyResveratrol-SR®) on vascular function, subclinical atherosclerosis and CV biomarkers**
- 2. Aim 2. Define adherence and barriers to compliance to supplementation.**

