#### **D. RESEARCH DESIGN AND METHODS AND DATA ANALYSIS**

**Research Design.** We will invite 56 women with an APO within the past 3 yrs to participate. Women will be randomly assigned to the 4-wk intervention group (n=28) or a standard care group (n=28) using a computerized random number generator, stratified by race. Assuming up to 25% with poor adherence, we expect that 42 women (21 each arm) will complete the study. No data exists related to effects of supplementation on vascular function in our population, we assumed a medium effect size, i.e. Cohen's  $d \sim 0.50$  and accepting a  $\beta=0.80$ , to generate sample sizes. Generation of effect sizes is a key outcome of this study. We will conduct a vascular assessment and blood draw at two visits: before the intervention begins and within 3 days of completing the intervention. We will conduct visits during the early follicular phase of menstrual cycle to account for fluctuating hormones. Vascular testing will be performed in the supine position and  $\geq 4$  hours after a light meal. Surveys for Aim 2 will be completed within the first 2 weeks of study enrollment, and interviews for Aim 2 will be conducted within 1 week of Visit 2, in-person or via telephone.

**Anti-inflammatory supplementation intervention.** Participants randomized to the supplementation intervention will receive PolyResveratrol-SR® (100 mg curcumin phytosome, 100 mg quercetin phytosome, 100 mg green tea phytosome, 100 mg trans-resveratrol, 100 mg trans-pterostilbene; Thorne Research). Participants will be asked to take 2 doses/day (1g total). Participants randomized to supplementation will receive a daily email reminding them to take the supplement. **Covariates.** Medical history, age, and sociodemographics will be obtained via self-report. We will use validated surveys to determine physical activity, sedentary behavior, and smoking history. Height and weight will be measured.

**Aim 1 Outcomes.** The outcomes will be measured in-person. All outcomes are listed and described below. [name] has extensive experience collecting the measurements described below.

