**Data Analyses.** We will calculate the 25th and 75th percentile for each biomarker and vascular function test and use these values as cut-offs for “low” and “high” levels, respectively. We will test for differences in biomarker levels between women by APO status and race using a t-test or Mann-Whitney U test, depending on the distribution of the variables. We will use separate multiple linear regression models to determine associations of each exposure (continuous levels of biomarkers; quartiles; and high or low levels of these biomarkers) with continuous measures of our outcomes (individual indices of vascular function, e.g. BP, arterial stiffness, augmentation index, FBF, endothelial function, and intima-media thickness) in all 56 women. We will use logistic regression to test for associations between continuous and categorical levels of biomarkers with categorical outcomes: the likelihood of having hypertension or prehypertension, high central arterial stiffness, low endothelial function, and high carotid intima-media thickness in all 56 women. We will test for unadjusted associations and then adjust all regression analyses for key co-variables: maternal age, race, and smoking. We will test for associations after furthering adjusting for years of education, body mass index (BMI), parity, and physical activity, in the index pregnancy in exploratory analyses. We will test for an interactive effect of APO status and race on these associations using a multiplicative interaction term in separate analyses and conduct all analyses stratified by APO status and/or race if the interaction is significant. We will conduct a sensitivity analysis by repeating our statistical tests only in the primiparous women as prior pregnancy is associated with lasting changes in vascular function and may influence our outcome and exposure variables.

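### The Data Analyses section never compares the supplement arm with standard care, so Aim 1 has no planned analysis

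*Combined protocol and SAP*

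**What the plan says.** Section A states Aim 1 as "Determine the effects of a 4-week course of anti-inflammatory supplementation" on vascular function, subclinical atherosclerosis and cardiovascular biomarkers. Section B describes a pilot trial that will test vascular and biomarker responses, with 28 women in each arm. The Research Design paragraph of Section D sets 1:1 randomisation stratified by race and the measurement times: "We will conduct a vascular assessment and blood draw at two visits: before the intervention begins and within 3 days of completing the intervention". It adds "Generation of effect sizes is a key outcome of this study".

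The Data Analyses paragraph of Section D then gives the analysis: "We will use separate multiple linear regression models to determine associations of each exposure". The exposures are biomarker levels (continuous, in quartiles, or high/low). The outcomes are blood pressure, stiffness, forearm flow, endothelial function and intima-media thickness, in all 56 women. The same paragraph plans tests of biomarker levels by APO status and race, logistic regressions on categorised outcomes, an APO-status-by-race interaction and a primiparous-only sensitivity analysis.

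The only other statistical text, under Aim 2 Outcomes, covers survey scores, one adherence proportion and interview coding.

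**The concern.** The aim and the design describe a two-arm randomised comparison with before-and-after measurements. The analysis describes an observational study of whether biomarker levels go with vascular indices. IL-6, IL-10, ICAM-1 and VCAM-1 are responses to treatment in Aim 1 but explanatory variables in the regressions.

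Three things are at stake.

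- The randomised contrast, which is the reason for running the trial, has no prespecified estimate or interval.
- If the gap is filled after the data are seen, the analyst chooses among Visit 2 difference, change score, baseline-adjusted difference and within-arm change, for each of about 15 measures.
- If Visit 2 values enter the pooled regressions, and the supplement affects both biomarkers and vascular indices, then arm is an unadjusted common cause and those associations are confounded by treatment.

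**Working it through.** **1. Search for the treatment contrast.** Each step of the Data Analyses paragraph, set against what Aim 1 needs:

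| Planned step | Groups or explanatory variable | Arm? | Visit 2, change or baseline outcome? |
|---|---|---|---|
| 25th/75th percentile cut-offs | none | no | no |
| t-test or Mann-Whitney on biomarkers | APO status, race | no | no |
| Linear regressions on vascular indices | biomarker level | no | no |
| Logistic regressions on categorised outcomes | biomarker level | no | no |
| Adjustment | age, race, smoking; then education, BMI, parity, activity | no | no |
| Interaction and stratified analyses | APO status by race | no | no |
| Sensitivity analysis | primiparous women only | no | no |

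The Aim 2 statistics contain no arm comparison either.

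**2. Does the text fit this trial?** Every participant has had an APO (Research Design; Section E.1), so the with/without-APO comparison and interaction cannot be run. The fallback extension to gestational diabetes adds another pregnancy history, not a group without an APO. The regressions use all 56 women, but the plan says "Assuming up to 25% with poor adherence, we expect that 42 women (21 each arm) will complete the study". Complete data on all 56 can be expected only at Visit 1. The paragraph reads as a plan for an observational study.

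**3. How many measures have no planned effect estimate?** Counting the Aim 1 Outcomes list: brachial SBP and DBP (2); central BP, augmentation index, end-systolic pressure and pulse wave velocity (4); forearm flow and conductance (2); peak and total reactive hyperaemia (2); intima-media thickness (1); four biomarkers (4). Total 2 + 4 + 2 + 2 + 1 + 4 = 15, with central BP counted once.

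**4. Can the intended contrast be inferred from the sample size?** The attrition step reproduces: 42/(1 − 0.25) = 56 and 21/(1 − 0.25) = 28. The effect-size step does not identify a contrast. I take d = 0.5, read the plan's β = 0.80 as 80% power, and assume two-sided alpha 0.05, since no alpha is stated.

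- Between arms: n = 2(1.96 + 0.8416)²/0.5² = 62.8, so 63 per arm (64 by exact t).
- Within one arm, paired t: 34.
- Baseline-adjusted between arms: 62.8(1 − r²) = 21 requires r = √(1 − 21/62.79) ≈ 0.82, which the plan does not state.

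None of these gives 21 or 28 without a further unstated assumption. A one-sided paired test needs 27, close to the 28 randomised but not to the 21 completing.

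**5. Why an effect size needs a named estimator.** Take a true between-arm difference of 0.5 SD and an assumed baseline–follow-up correlation r = 0.7. The same difference becomes:

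- divided by the Visit 2 SD: 0.50;
- divided by the change-score SD, √(2(1 − 0.7)) = 0.775: 0.5/0.775 = 0.65;
- divided by the ANCOVA residual SD, √(1 − 0.49) = 0.714: 0.5/0.714 = 0.70.

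**6. Precision available from the Visit 1 data.** ANCOVA leaves a fraction 1 − r² of the variance, a reduction of 25% at r = 0.5 and 49% at r = 0.7. Power uses the noncentral t with noncentrality [0.5/√(1 − r²)]·√(n/2) and df = 2n − 3. At n = 21 and r = 0.5 the noncentrality is (0.5/0.866) × 3.240 = 1.87. The Visit 2 t-test (df = 2n − 2) has 0.5 × 3.240 = 1.62.

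| Analysis (d = 0.5, two-sided 0.05) | 21 per arm | 28 per arm |
|---|---|---|
| Visit 2 t-test | 35% | 45% |
| ANCOVA, r = 0.3 | 38% | 49% |
| ANCOVA, r = 0.5 | 45% | 56% |
| ANCOVA, r = 0.7 | 60% | 73% |
| Change score, r = 0.5 | 35% | 45% |
| Change score, r = 0.7 | 53% | 66% |

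**The case against.** The best defence is that the arm comparison is declared, only not written out. Section B proposes to test responses to supplementation with 28 women per arm, Section D assumes a Cohen's d, and effect sizes are called a key outcome. On that reading a sensible analyst would report an arm difference anyway, and a pilot need not specify more.

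The intent is real, and it is fair to say the protocol as a whole promises effect sizes. But neither sentence gives a contrast, model or estimator, and the one detailed analysis supplied answers a different question. Being a pilot makes this worse, since effect sizes are what it is meant to deliver.

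Three narrower points stand:

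- The power figures compare two analyses that are both absent from the plan. They show the gain from using Visit 1 data, not the size of the omission, and at r = 0.3 the gain is small.
- The confounding concern is conditional. The plan does not say which visit feeds the regressions, and at Visit 1 arm cannot confound them.
- A change-score comparison or a mixed model would also answer Aim 1. ANCOVA is recommended for its precision and is not the only valid choice.

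**Conclusion.** The concern holds and must be fixed. The Data Analyses section specifies no between-arm analysis for any of the 15 or so Aim 1 measures, and part of what it does specify cannot be run because all participants have had an APO. This conclusion rests on the text alone. The power and effect-size figures are supporting illustrations that assume two-sided alpha 0.05 and r between 0.3 and 0.7, neither of which the documents give. The mismatch between the stated sample size and d = 0.5 at 80% power is a separate matter and is not needed here.

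**What to change.** Make this the lead analysis in the Data Analyses section:

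- For each Aim 1 outcome, fit a linear model (ANCOVA) of the Visit 2 value on randomised arm, adjusting for the Visit 1 value of that outcome and for race, the stratification factor.
- Analyse women in the arm to which they were assigned, whatever their pill count. Say how the women without a Visit 2 value (14 of 56 on the plan's own assumption) are handled.
- Report the adjusted mean difference, its 95% CI and a standardised effect size, naming the SD used as the divisor. Log-transform skewed biomarkers.
- Keep the biomarker–vascular regressions as secondary analyses of Visit 1 data only, and remove the comparisons and interaction by APO status.

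Naming one primary vascular outcome at the same time would settle which of the 15 estimates leads.

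The cost is a rewritten paragraph. The data, visits and participants are already planned.

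### Percentile-cut vascular outcomes leave the logistic models at most 14 events: less power than the planned linear models, and quartile odds ratios sometimes not estimable, possibly often in primiparous women

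*Combined protocol and SAP*

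**What the plan says.** All of this is in Section D, under Data Analyses.

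- The 25th and 75th percentiles are calculated as the "percentile for each biomarker and vascular function test and use these values as cut-offs for" low and high levels.
- Linear models relate each biomarker (continuous, in quartiles, and as high or low) "with continuous measures of our outcomes (individual indices of vascular function", in all 56 women.
- The next sentence repeats the exercise with categories: "We will use logistic regression to test for associations between continuous and categorical levels of biomarkers with categorical outcomes". Besides hypertension or prehypertension, the outcomes are "high central arterial stiffness, low endothelial function, and high carotid intima-media thickness in all 56 women".
- The plan will then "adjust all regression analyses for key co-variables: maternal age, race, and smoking". Exploratory models add education, BMI, "parity, and physical activity, in the index pregnancy in exploratory analyses".
- Finally: "We will conduct a sensitivity analysis by repeating our statistical tests only in the primiparous women".

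The section gives no event count or power for these models, no method for sparse data, and no rule for which result counts if the linear and logistic models disagree. Section E.1 excludes current smokers, so the smoking covariate can only carry past smoking.

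**The concern.** A cut at a sample quartile fixes the event fraction at one quarter, however the measurements fall. That has two consequences.

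First, information is discarded on an outcome that the same section already models in full. A null odds ratio for high stiffness could then be set against a positive linear result for the same variable, with nothing in the plan to say which to believe.

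Second, with so few events a biomarker quartile may contain none. Its maximum-likelihood odds ratio is then zero or infinite (or, if it is the reference quartile, all three are infinite), and the printed value depends on where the software stops iterating. This is likeliest in the primiparous subset, the analysis meant to show robustness.

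**Working it through.** The plan states no figure for these models, so there is none to reproduce. Its sample-size statement (Cohen's d of about 0.50) concerns supplementation effects, not these associations.

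**Events.** 0.25 × 56 = 14 if every woman is measured and there are no ties; missing measurements lower this. If each covariate takes one slope (an assumption, since coding is not given):

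- Core models have 4 slopes with a continuous or high/low biomarker and 6 with quartiles: 14/4 = 3.5 and 14/6 = 2.3 events per slope.
- Exploratory models have 8 to 10 slopes: 14/8 = 1.75 to 14/10 = 1.4.
- If smoking were coded as current status it would be constant and drop out: 14/3 = 4.7 for the smallest core model.

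**Power.** The large-sample efficiency of a 75th-percentile cut is φ(z)²/[p(1−p)], with p = 0.25 and φ(z) = 0.318: 0.318²/0.1875 = 0.54. Simulated power for 56 women follows (bivariate normal, three covariates unrelated to either variable, two-sided 5% level; the correlations, the level and the covariate frequencies are assumptions):

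| Correlation | Linear | Outcome cut | Outcome and biomarker cut |
|---|---|---|---|
| 0.25 | 45% | 31% | 19% |
| 0.35 | 75% | 50% | 32% |
| 0.45 | 93% | 75% | 49% |

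At 0.35, the linear and outcome-cut figures become about 57% and 42% with a lognormal biomarker, and 50% and 40% with both variables lognormal. The direction holds and the gap narrows.

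**Quartile coding, all 56 women, unadjusted.** There are 14 women per quartile and 14 events. With no association, the exact chance that some quartile has no event is

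[4·C(42,14) − 6·C(28,14) + 4·C(14,14)] / C(56,14) = 0.036.

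By simulation it is 10%, 17% and 29% at correlations of 0.25, 0.35 and 0.45. When the top-versus-bottom odds ratio can be estimated, the median ratio of its upper to lower 95% limit is about 37 to 44 for correlations up to 0.37.

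**High/low coding.** With no association, the chance that the high group has no event is C(42,14)/C(56,14) = 0.009, so separation is rare.

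**Primiparous women, quartile coding, unadjusted.** The share is not given, so a range is shown. Parity is assumed unrelated to either variable. With cut-offs recomputed, 28 women give 7 events and 40 give 10. With no association the exact values are

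- 28 women: [4·C(21,7) − 6·C(14,7) + 4·C(7,7)] / C(28,7) = 0.375
- 40 women: [4·C(30,10) − 6·C(20,10) + 4·C(10,10)] / C(40,10) = 0.140

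| Women | Recomputed cut-offs: none / 0.35 | Full-sample cut-offs: none / 0.35 |
|---|---|---|
| 22 | 51% / 63% | 67% / 76% |
| 28 | 37% / 56% | 46% / 61% |
| 34 | 28% / 47% | 30% / 48% |
| 40 | 14% / 33% | 19% / 36% |

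(None = no association; 0.35 = correlation of 0.35.) The plan does not say which cut-offs the subset would use.

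**Bias with a continuous biomarker.** At 0.35 with core covariates, the large-sample log odds ratio is 0.638. Maximum likelihood averages 0.750 (+18%) with an SD of 0.449, so the bias is (0.750 − 0.638)/0.449 = 0.25 SD. Wald 95% coverage is 95%. Firth penalisation averages 0.644.

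**The case against.** The strongest reply is that this is a pilot, these are secondary associations, and the better-powered linear models are already planned and lose nothing. That stands, and it caps the weight of the point. It does not remove it: Section D calls generating effect sizes a key outcome, and an infinite odds ratio is of no use for that.

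A second reply is that quartiles are named only in the linear-regression sentence. The logistic sentence speaks of categorical levels, which high/low coding alone would satisfy. This also stands in part. Quartiles are the natural reading because the preceding sentence lists them, but it is a reading. If only high/low coding is meant, the separation problem largely disappears and the power loss remains.

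Third, the power gap rests on assumed correlations and on normality, while the plan itself allows for non-normal variables by naming a Mann-Whitney alternative. The skewed-variable figures above concede this.

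A reader might also infer that quartile odds ratios often fail in the full sample. The figures do not support that: at correlations up to 0.35, at least 83% of unadjusted full-sample fits are finite. Nor do the documents support taking half the women as primiparous; that share is unknown. Finally, the few events per slope might suggest that odds ratios for a continuous biomarker mislead. In the full sample, with bias of about a quarter of an SD and near-nominal coverage, they are imprecise rather than misleading.

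**Conclusion.** The point holds as a minor one. The limit of 14 events follows from the percentile rule and 56 women, and needs no further assumption. The loss of power is certain in direction. Its size (75% to 50% at a correlation of 0.35) rests on the assumed correlation and normality. Quartile odds ratios are sometimes not estimable in all 56 women. In primiparous women they may often not be: with recomputed cut-offs, between no association and a correlation of 0.35, 37% to 56% for 28 women but 14% to 33% for 40. Both statements depend on quartiles being used in the logistic models.

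Hypertension or prehypertension stands apart: it is not a percentile cut, and its event count cannot be derived from the document. Nothing here bears on the comparison of the randomised arms.

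**What to change.** - State that the linear models of the continuous vascular indices, with continuous biomarkers and the core covariates, govern the conclusion, including in the primiparous sensitivity analysis.
- Drop the percentile-cut logistic models for stiffness, endothelial function and intima-media thickness. Alternatively, keep them as descriptive only, fitted with Firth penalisation, preferably with a continuous biomarker, and with at most the core covariates.
- For hypertension or prehypertension, limit model size by the observed number of events and use Firth penalisation if events are sparse.
- Define the smoking covariate as past smoking, since current smokers are excluded.

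Quartile and high/low biomarker codings may stay in the linear models as supplementary analyses. The cost is a few sentences of analysis-plan wording and slightly less analysis work, with no new data. The downside is fewer high/low odds ratios to report.

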## **B. BACKGROUND AND SIGNIFICANCE**

Adverse pregnancy outcomes (APOs) occur in up to 20% of all pregnancies and are associated with a lifetime of higher cardiovascular disease (CVD) risk. **Aberrant and persistent systemic inflammation is a hallmark of both APOs and CVD.** An inappropriate uterine innate immune response to invading fetal cytotrophoblasts is thought to underlie poor placentation and vascular-related APOs; inflammation of the uterine cavity evokes contractions and contributes to preterm birth. Levels of cytokines involved in endothelial inflammation, an instigating event in hypertensive and atherosclerotic processes, were higher in the 2nd trimester in women destined to have APOs. Women with a past APO have higher levels of systemic inflammation, including c-reactive protein and interleukin-6 (IL-6), in the years after delivery versus women with no APOs. A similar pro-inflammatory cytokine profile has been observed in patients with overt CVD. **Intervening on systemic inflammation may be a viable strategy to interrupt the progression from APO to CVD.**

Dietary supplements, such as polyphenols, are anti-inflammatory and inhibit vascular inflammation with potentially few barriers to adherence. **Given the hypothesized contribution of a persistent pro-inflammatory state to the excess CVD risk observed in women after APO, utilization of a polyphenol dietary supplement to specifically target inflammation holds promise as a low-burden intervention to prevent or delay APO-related CVD.** To our knowledge, efficacy and tolerability of a dietary polyphenol supplement has not been investigated in women with a history of APO. To fill in this critical gap in knowledge, we propose to test the vascular function and CV biomarker, i.e., IL-6, IL-10, intracellular and vascular cell adhesion molecule-1 (ICAM-1 and VCAM-1), responses to a 4-week anti-inflammatory dietary supplementation in a clinical trial pilot study of 56 women, 28 assigned to the intervention and 28 to the control group, in the first 3 years after an APO.

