## **E. PROTECTION OF HUMAN SUBJECTS**

### **1. TARGET POPULATION:**

**Participants and incentives.** We will invite women who had a vascular APO 6 months-3 years ago and were 18 years or older at the time of the APO, to participate. Exclusion criteria: currently pregnant or breastfeeding, current smoking, active cancer, regular use of NSAIDs, steroid medications, statins, or other anti-inflammatory supplements, HIV/AIDS, uncontrolled high blood pressure, unwilling or unable to use a dietary supplement, known sensitivity to resveratrol, curcumin, green tea, or quercetin. We will provide a cash incentive of \$50 after study Visit 1 and Visit 2. If enrollment numbers are below target at 6-months, we will open enrollment to women with a history of gestational diabetes (GDM) as GDM is also associated with inflammation and excess CVD risk in women. We chose the time interval of 6 months to 3 years after delivery because it takes about 6 months to return a pre-pregnancy physiological state, but vascular dysfunction has been documented for at least 3 years after an APO.

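### Time since the index APO delivery can vary six-fold but is in neither covariate set of the biomarker–vascular regressions; add it to the linear models

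*Combined protocol and SAP*

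**What the plan says.** The Data Analyses paragraph of section D plans separate linear regressions of each vascular index on each biomarker, with the biomarker taken as continuous, in quartiles, and as high or low. All 56 women are pooled. The models are fitted unadjusted, and the plan will then "adjust all regression analyses for key co-variables: maternal age, race, and smoking". Exploratory models go on to "furthering adjusting for years of education, body mass index (BMI), parity, and physical activity". Logistic models for categorical outcomes use the same covariates.

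Section E.1 (Target Population) sets the entry window: "We will invite women who had a vascular APO 6 months-3 years ago". It gives two reasons for that window: "it takes about 6 months to return a pre-pregnancy physiological state", and "vascular dysfunction has been documented for at least 3 years after an APO". The Research Design paragraph of section D gives only the upper limit: "We will invite 56 women with an APO within the past 3 yrs to participate".

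Two other statements bear on the point. The Data Analyses paragraph justifies a sensitivity analysis in primiparous women on the ground that an earlier pregnancy leaves lasting vascular changes and could affect both the exposures and the outcomes. Section B (Background and Significance) reports higher inflammation in women with a past APO "in the years after delivery versus women with no APOs".

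**The concern.** Two women in the same regression can differ by 30 months in time since the index delivery. The plan treats that interval as relevant enough to define eligibility, and it accepts that a woman's pregnancy history may act on both sides of these regressions. It then deals with whether there was an earlier pregnancy, but not with how long ago the index one ended. Time since delivery is not a stratification factor either; randomisation is stratified by race only.

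The exposure here is a measured biomarker, so these are observational associations within a trial population. If a biomarker and a vascular index both drift with time after delivery, part or all of their association could reflect elapsed time, and the models as listed could not separate the two. What is at stake is the interpretation of the biomarker–vascular associations, not the estimated effect of the supplement.

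**Working it through.** **Inputs from the documents**
- Window: 6 to 36 months (section E.1). 36 / 6 = 6, a range of up to six-fold.
- Regression sample: n = 56 (section D, Data Analyses).
- Named covariates: 3 main (age, race, smoking) plus 4 exploratory (education, BMI, parity, physical activity) = 7. Number that are time since delivery: 0.

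**Input that is assumed**
- The correlation r of time since delivery with the biomarker and with the vascular index, taken as equal for both and as what remains after the listed covariates. The documents give no value, so a range is shown.

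The plan states no power, precision or confounding figure for these regressions, so there is none to reproduce.

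**Formula.** Suppose the biomarker and the vascular index have no direct association and each correlates r with time. The correlation induced between them is r × r. With Fisher's z, the chance of declaring an association at two-sided 0.05 is

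Φ(−1.96 + δ) + Φ(−1.96 − δ), where δ = atanh(r²) × √(56 − 3) and √53 = 7.280.

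For r = 0.3: r² = 0.09, atanh(0.09) = 0.0902, δ = 0.657. The probability is Φ(−1.303) + Φ(−2.617) = 0.096 + 0.004, about 0.10.

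The other values follow in the same way. A simulation of 40,000 data sets per row at n = 56 gives the last two columns.

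| Assumed r | Induced r² | Fisher z | Simulated, time omitted | Simulated, time included |
|---|---|---|---|---|
| 0.1 | 0.01 | 5.1% | 5.1% | 5.0% |
| 0.2 | 0.04 | 6.0% | 6.2% | 5.2% |
| 0.3 | 0.09 | 10.1% | 10.1% | 4.9% |
| 0.4 | 0.16 | 21.7% | 21.8% | 5.1% |

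Including time returns the rate to about 5% in every row.

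**Cost in the linear models** (race counted as one term). The main model has an intercept, biomarker, age, race and smoking: 56 − 5 = 51 residual degrees of freedom, or 50 with time added. The exploratory model goes from 56 − 9 = 47 to 46.

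**Cost in the quartile-cut logistic models.** A cut at the 25th or 75th percentile gives 56 × 0.25 = 14 events.
- Main set, 4 parameters besides the intercept: 14 / 4 = 3.5 events per parameter, falling to 14 / 5 = 2.8 with time added.
- Exploratory set, 8 parameters: 14 / 8 = 1.75, falling to 14 / 9 = 1.56.

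The event count for the hypertension or prehypertension outcome cannot be derived from the documents.

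**The case against.** A reader might infer that the plan itself describes recovery across the 6 to 36 month window, so that shared recovery time must drive the associations. The text does not support this. Section E.1 puts the return to the pre-pregnancy state at about 6 months, which is where the window opens, and says that dysfunction has been documented for at least 3 years, which covers the whole window. The statement in section B is a contrast between women with and without an APO, not a trend over time. No section gives a trend for any biomarker or vascular index between 6 and 36 months.

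Further arguments on the other side:

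- **The design already limits early postpartum variation.** The 6-month floor, the exclusion of pregnant and breastfeeding women and the early follicular visit timing all restrict it. This stands, and it makes a strong time effect less likely. It does not address variation between 6 and 36 months.
- **The size is entirely assumed.** This stands. At r = 0.1 nothing changes, and only sizeable correlations with both variables matter.
- **Multiplicity is the larger issue for these analyses.** Four biomarkers × three codings × at least six vascular indices gives at least 72 linear models before the adjustment tiers, with no multiplicity control stated. This tempers how much any one association can be trusted, but it is not a reason to leave out an inexpensive covariate.
- **Aim 1 is the randomised effect of supplementation.** Time since delivery cannot confound that contrast except by chance imbalance. This stands. The Data Analyses paragraph lists no between-arm model to which a covariate could be added, so the point is confined to the observational regressions.

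**Conclusion.** The omission is confirmed: time since the index APO delivery is in neither covariate set, although it defines eligibility and can vary six-fold. Confounding of the pooled biomarker–vascular associations is therefore possible, but the documents do not show that it occurs. What supports raising it is limited to two things: the plan's use of this interval to choose its population, and its own acceptance that an earlier pregnancy may influence both exposure and outcome.

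The false-positive figures of about 6%, 10% and 22% rest wholly on assumed equal correlations of 0.2, 0.3 and 0.4, no direct association, and n = 56 analysed. This is a minor, inexpensive improvement to secondary analyses. It does not bear on the validity of the randomised comparison.

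**What to change.** In the Data Analyses paragraph of section D, add to the key co-variables of the linear regression models: months from the index APO delivery to the visit at which the analysed measures are taken, as a continuous term. The interval should be tied to that visit because the paragraph does not say whether Visit 1 or Visit 2 measures enter the regressions. Counting from the index APO delivery matches the eligibility window, so the date should already be established for each woman at screening. If the sponsor prefers to leave the variable out, a sentence of justification would serve.

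The cost is a few words and one degree of freedom per linear model. The quartile-cut logistic models should be left out of this change: with about 14 events they are already too sparse for a further covariate.
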